# 16. EFFICACY OUTCOMES

Unless otherwise stated, the primary efficacy analyses will be based on the FAS with Baseline MMS 5 to 9. Primary and secondary efficacy analyses will be repeated for all participants in FAS with Baseline MMS 4 to 9 as supplementary analysis.

The following definitions will be used to assess efficacy outcomes:

- Clinical remission: SF subscore = 0 (or = 1 with a ≥ 1-point decrease from baseline), RB subscore = 0, and ES ≤ 1 (excluding friability)
- Endoscopic improvement: ES ≤ 1 (excluding friability)
- Symptomatic remission: SF subscore = 0 (or = 1 with a ≥ 1-point decrease from baseline) and RB subscore = 0
- Mucosal healing: ES ≤ 1 (excluding friability) with histologic remission measured by a Geboes Index score
   < 2.0

- Clinical response: A ≥ 2-point and ≥ 30% decrease from baseline in MMS, and a ≥ 1-point decrease from
  baseline in RB subscore or an absolute RB subscore ≤ 1
- Endoscopic normalization: ES = 0
- Complete symptomatic remission: SF subscore = 0 and RB subscore = 0
- Noninvasive clinical response: A ≥ 30% decrease from baseline in composite RB and SF, and a ≥ 1-point decrease from baseline in RB subscore or an absolute RB subscore ≤ 1
- Symptomatic response: Decrease from baseline ≥ 30% in composite RB and SF subscores
- Clinical remission using TMS: TMS of ≤ 2 points with no individual subscore of > 1 point
- Clinical response using TMS: A ≥ 3-point and ≥ 30% decrease from baseline in TMS, and a ≥ 1-point decrease from baseline in RB subscore or an absolute RB subscore ≤ 1
- Histologic improvement using Geboes Index: Geboes Index score < 3.1

- Histologic remission using Geboes Index: Geboes Index score < 2.0

- Histologic improvement using Robarts Histopathology Index (RHI): ≥ 50% reduction from Baseline in RHI or RHI ≤ 3
- Histologic remission using RHI: RHI ≤ 3, with scores of 0 (zero) for both Geboes Grade 2B (lamina propria

Document: \quintiles.net\enterprise\Apps\sasdata\SASb\SAS\Arena\APD334\RZA28116\Biostatistics\Documenta

tion\SAP\503-Final SAP v2.0\APD334-203\_SAP\_Final v2.0-20231120\_clean.docx

Author: PPD Version Number: 2.0

Version Date: 20Nov2023

Template No.: CS\_TP\_BS016 Revision 7 Reference: CS\_WI\_BS005

Effective Date: 01Nov2021

Page 34 of 70

neutrophils) and Grade 3 (neutrophils in epithelium)

- Histologic improvement using Nancy Histologic Index (NHI): ≥ 1 point reduction from Baseline NHI
- Histologic remission using NHI: ≤1
- Improvement in extraintestinal manifestations (EIMs): any category improved at post-baseline

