4.1. Inclusion Criteria

Participants must meet ALL of the following inclusion criteria to be eligible for enrollment into the study:

1. Japanese ancestry (ie, both parents and 4 grandparents are/were of Japanese descent)
2. 18 to 80 years of age, inclusive, at the time of consent
3. Ability to provide written informed consent and to be compliant with the schedule of protocol assessments

Disease-specific inclusion criteria:

4. Diagnosed with UC \geq 3 months prior to screening. The diagnosis of UC must be confirmed by endoscopic and histologic evidence. The endoscopy and histology report should be present in the

source documents; however, if not available, the screening endoscopy and histology may serve as such.

5. Active UC confirmed by endoscopy with ≥ 10 cm rectal involvement
6. Moderately to severely active UC defined as MMS of 4 to 9, including an ES ≥ 2 and RB subscore ≥ 1
7. Received a surveillance colonoscopy (performed according to local standard) within 12 months before baseline to rule out dysplasia in participants with pancolitis > 8 years duration or participants with left-sided colitis > 12 years duration. Participants without a surveillance colonoscopy within the prior 12 months will have a colonoscopy at screening (ie, in place of screening proctosigmoidoscopy). Any adenomatous polyps must be removed according to routine practice prior to their first dose of study treatment.

Prior treatment:

8. Demonstrated an inadequate response to, loss of response to, or intolerance to at least 1 of the following therapies as defined below:
 - Conventional therapy
 - a. Oral 5-ASA compounds
 - b. Systemic (oral or IV) Corticosteroids
 - c. Thiopurines (eg, AZA, or 6-MP)
 - Biologics or JAK inhibitors
 - a. Anti-TNF α antibodies (eg, infliximab, adalimumab, golimumab or biosimilars)
 - b. Anti-integrin antibodies (eg, vedolizumab, carotegrast methyl)
 - c. Anti-interleukin-12/23 antibodies (eg, ustekinumab)
 - d. JAK inhibitors (eg, tofacitinib)

Inadequate response, loss of response, and intolerance are defined as:

- Inadequate response: Signs and symptoms of persistently active disease despite a history of completing a dosing regimen
- Loss of response: Recurrence of symptoms of active disease during treatment following prior clinical benefit (discontinuation despite clinical benefit does not qualify as having failed or being intolerant to UC biologic therapy)

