9.8.1.2. Endoscopic Biopsies

Per inclusion criteria (Section 4.1), a histopathology report supporting the diagnosis of UC must be available in the source documents prior to randomization. Post-randomization detected polyps or suspicious findings during endoscopy will be managed as per local standard of care. If a histopathology report is not available, the screening endoscopy may serve as such with histology evaluated at the local histology laboratory.

Biopsies will be obtained at each endoscopy to support assessment of the histopathology endpoints and, where permitted, for the assessment of exploratory biomarkers. Up to 2 biopsy pairs (ie, total 4) will be collected from the most affected area 10 to 25 cm from the anal verge. Samples should be collected, stored, and shipped as described in the laboratory manual.

The original location (colonic segment) of biopsy specimens acquired at screening must be clearly indicated. Detailed instructions for endoscopic biopsies (eg, number of biopsies, anatomic site, normal or inflamed mucosa) will be provided.

Biopsy samples will be processed by a central laboratory and histopathologic scoring using the Geboes, Robarts, and Nancy histopathology indices (Appendix 4) will be performed by a blinded central histopathology reader (Geboes 2000, Marchal-Bressenot 2017, Mosli 2017).

Biopsy specimen transfer, processing, slide preparation and digitization of slides for histopathologic scoring procedures will be detailed in a histopathology manual. Histopathology results will not be made available to study sites.

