10.5. Efficacy Endpoint Definitions

The following definitions will be used to assess efficacy outcomes. Summary scores calculated from the components of the MMS and its component subscores will be used to assess efficacy.:

- Clinical remission: SF subscore = 0 (or = 1 with a ≥ 1 point decrease from baseline), RB subscore = 0, and ES ≤ 1 (excluding friability)
- Endoscopic improvement: ES ≤ 1 (excluding friability)
- Symptomatic remission: SF subscore = 0 (or = 1 with a ≥ 1 point decrease from baseline) and RB subscore = 0
- Mucosal healing: ES ≤ 1 (excluding friability) with histologic remission measured by a Geboes Index score < 2.0
- Clinical response: A ≥ 2 -point and $\geq 30\%$ decrease from baseline in MMS, and a ≥ 1 -point decrease from baseline in RB subscore or an absolute RB subscore ≤ 1
- Endoscopic normalization: ES = 0
- Complete symptomatic remission: SF subscore = 0 and RB subscore = 0
- Noninvasive clinical response: A $\geq 30\%$ decrease from baseline in composite RB and SF, and a ≥ 1 point decrease from baseline in RB subscore or an absolute RB subscore ≤ 1
- Symptomatic response: Decrease from baseline $\geq 30\%$ in composite RB and SF subscores
- Clinical remission using TMS: TMS of ≤ 2 points with no individual subscore of > 1 point
- Clinical response using TMS: A ≥ 3 -point and $\geq 30\%$ decrease from baseline in TMS, and a ≥ 1 -point decrease from baseline in RB subscore or an absolute RB subscore ≤ 1
- Histologic improvement: Geboes Index score < 3.1
- Histologic remission: Geboes Index score < 2.0

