#### 16.3.1. Exploratory Efficacy Variables and Derivations

Exploratory efficacy endpoints are:

- The proportion of participants achieving symptomatic remission at Weeks 2, 4, 8
- The proportion of participants achieving complete symptomatic remission at each study visit (Weeks 2, 4, 8, 12)
- The proportion of participants achieving noninvasive clinical response at each study visit (Weeks 2, 4, 8, 12)
- The proportion of participants achieving symptomatic response at each study visit (Weeks 2, 4, 8, 12)
- The proportion of participants with remission and response using TMS at Week 12
- The proportion of participants with histologic improvement at Week 12 (as defined by the Geboes Index, Robarts Histopathology Index, and Nancy Histologic Index)
- The proportion of participants with histologic remission at Week 12 (as defined by the Geboes Index, Robarts Histopathology Index, and Nancy Histologic Index)
- The proportion of participants with improvement in extraintestinal manifestations (EIMs) at Week 12 in participants with EIMs at baseline

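### The SAP's Geboes and RHI improvement rules credit participants already below the cut-off at baseline, and its EIM rule ignores concurrent worsening

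*SAP*

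**What the plan says.** SAP Section 16 gives three definitions of histologic improvement:

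- RHI: "Histologic improvement using Robarts Histopathology Index (RHI): ≥ 50% reduction from Baseline in RHI or RHI ≤ 3"
- Geboes: "Histologic improvement using Geboes Index: Geboes Index score < 3.1". This carries over Protocol 10.5, "Histologic improvement: Geboes Index score < 3.1".
- Nancy: "Histologic improvement using Nancy Histologic Index (NHI): ≥ 1 point reduction from Baseline NHI"

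For EIMs the same section says "Improvement in extraintestinal manifestations (EIMs): any category improved at post-baseline". The endpoint list in SAP 16.3.1 supplies the population and the timepoint: "The proportion of participants with improvement in extraintestinal manifestations (EIMs) at Week 12 in participants with EIMs at baseline".

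SAP 16.3.3 analyses all of these in the mFAS with baseline MMS 5 to 9. Under SAP 5.5 the mFAS needs a baseline measurement to exist; it does not need that measurement to show activity. Eligibility (Protocol 4.1) is set on MMS, endoscopic score and rectal bleeding, with no histologic threshold. SAP 3.3 lists the RHI, Nancy and EIM definitions as additions made by the SAP.

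**The concern.** An improvement endpoint should need a change for the better. The Geboes rule and the second clause of the RHI rule describe a state at Week 12 instead. An absolute threshold does no harm where entry guarantees that everyone starts on the wrong side of it. Endoscopic improvement is safe for that reason: it needs a score of 1 or less, and entry requires 2 or more. Histology has no such guard.

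The three indices are reported as parallel versions of one endpoint. An unchanged low-activity biopsy would be improved on RHI and Geboes but not improved on Nancy.

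The EIM problem is different. Someone must have EIMs at baseline and must improve in at least one category, but the definition says nothing about the other categories. A cleared eye finding with new joint disease counts as improvement.

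At stake are inflated proportions in all groups, a diluted treatment difference for Geboes and RHI, and an EIM proportion that can rise while some participants are worse overall.

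**Working it through.** The plan gives no figure for this point, so the check is an enumeration of the rules followed by an illustration.

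**RHI.** Protocol Appendix 4 gives the weights 1, 2, 3 and 5 and a range of 0 to 33. With each component scored 0 to 3, the maximum is 3 × (1 + 2 + 3 + 5) = 33, which reproduces the stated range. All 34 integer scores from 0 to 33 are attainable. Taking every baseline and Week 12 pair and keeping those credited although Week 12 is not below baseline:

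- Baseline 0: Week 12 of 0, 1, 2 or 3 (4 pairs)
- Baseline 1: 1, 2 or 3 (3 pairs)
- Baseline 2: 2 or 3 (2 pairs)
- Baseline 3: 3 (1 pair)

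That is 10 pairs, 4 unchanged and 6 worse. With baseline above 3 there are none, because both clauses then force a fall.

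**Geboes.** Any baseline below 3.1 that is unchanged, or rises but stays below 3.1, is credited.

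**Nancy.** No unchanged or worsened pair is credited.

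**EIMs.** Table 6, footnote o, names four systems (eyes, liver, skin, joints). Treating each as a category that can be better, the same or worse (worse includes new) gives 3^4 = 81 patterns.

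- No category better: 2^4 = 16, so 81 − 16 = 65 are credited.
- Credited with none worse: 2^4 − 1 = 15, so 65 − 15 = 50 credited patterns include a worsening.
- More worse than better: one better and two worse (12 patterns) plus one better and three worse (4 patterns) = 16.

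These are counts of possible patterns, not probabilities.

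**Illustrative size for RHI or Geboes.** Let p be the true improvement proportion among participants with active baseline histology. Let q be the share who start within the cut-off and stay there, taken as equal across groups. The reported proportion is (1 − q)p + q, and the reported difference is (1 − q) times the true one. Assume p = 25% on placebo and 45% on etrasimod, a 20-point difference, and q from 5% to 20%. None of these values is in the documents.

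| q | Placebo | Etrasimod | Difference |
|---|---|---|---|
| 5% | 0.95 × 25 + 5 = 28.8% | 0.95 × 45 + 5 = 47.8% | 19 points |
| 20% | 0.80 × 25 + 20 = 40% | 0.80 × 45 + 20 = 56% | 16 points |

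At the planned 32 per group, q of 5% or 20% is 32 × 0.05 = 1.6 or 32 × 0.20 = 6.4 participants per group.

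**What a repair of the clause alone would do.** If low-baseline participants are no longer credited but stay in the denominator, the proportion is (1 − q)p. At q = 5% this gives 23.8% versus 42.8%, still 19 points. At q = 20% it gives 20% versus 36%, still 16 points. The false credit stops but the dilution remains. Only a denominator of baseline-active participants returns the 20 points.

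**The case against.** The strongest reply is that low baseline histology should be uncommon. Entry needs a centrally read endoscopic score of at least 2, and Protocol 9.8.1.2 directs sampling to the worst mucosa in range: "Up to 2 biopsy pairs (ie, total 4) will be collected from the most affected area 10 to 25 cm from the anal verge". This stands as a limit on frequency. It does not exclude the case, because entry asks only for "Active UC confirmed by endoscopy with ≥ 10 cm rectal involvement", so in limited disease the sampled segment can lie at or beyond the margin. The proctitis subgroup in SAP 8.5 shows that limited disease is anticipated, but it says nothing about baseline RHI or Geboes values.

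The reply on materiality also stands. The endpoints are exploratory, SAP 6.5 allows no tests, and with equal q the error works against etrasimod. SAP 16.3.2 sets missing data and intercurrent events to nonresponse, so not every low-baseline participant is credited. A shift of 1 to 4 points is small beside a 95% interval half-width of about 23 points: 1.96 × √(0.25 × 0.75/32 + 0.45 × 0.55/32). The actual groups will be smaller because of the early stop.

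A reader might infer three stronger things that the documents do not support.

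- **That all the histologic-improvement rules are faulty.** Nancy is not.
- **That the EIM rule lacks a baseline requirement or credits people with no improvement.** SAP 16.3.1 restricts it to participants with EIMs at baseline, and at least one category must improve.
- **That off-drug EIM findings could enter.** Table 6 marks EIM checks at the follow-up visits, and Section 16 says only post-baseline. But SAP 16.3.1 fixes Week 12, SAP 6.4 keeps the follow-up visits outside the visit windows, and footnote o places these examinations at screening and Week 12/ET.

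**Conclusion.** The point holds in a narrow form. As written, the Geboes rule and the RHI ≤ 3 clause count some unchanged or worsened participants as improved: for RHI, 10 score pairs, all with baseline 3 or lower. The EIM rule can count a participant with mixed or net worsening as improved, and the SAP does not define category or improved for EIMs. Nancy needs no change.

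The fall from 20 to between 19 and 16 points rests entirely on the assumed 25% and 45%, on q of 5% to 20%, and on q being equal across groups. In small groups q could differ by chance, and the error could then go either way. Nothing in the documents lets the real size be estimated.

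The fault does not reach the secondary mucosal-healing endpoint, which also requires an endoscopic score of 1 or less from an entry score of at least 2. No primary or secondary conclusion depends on this, so it is a low-priority correction.

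**What to change.** Amend SAP 16 and 16.3.3 before unblinding and record the change in SAP 3.3.

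- **Geboes and RHI improvement:** analyse in participants with baseline activity (Geboes ≥ 3.1 for the Geboes endpoint, RHI > 3 for the RHI endpoint). This removes both the false credit and the dilution.
- **At minimum for RHI:** let the RHI ≤ 3 clause count only when baseline RHI exceeds 3 or the score has fallen from baseline. This takes the 10 miscredited pairs to 0 but leaves the dilution.
- **EIMs:** define improvement as at least one baseline category improved at the Week 12 analysis visit with no category new or worsened, and state what counts as a category and as improved. This removes the 50 credited patterns that contain a worsening.
- **Nancy:** leave unchanged.

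The cost is wording, plus slightly smaller denominators for exploratory endpoints in a study that is already short of its planned size.

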# 16.1. Primary Efficacy

## 16.1.1. Primary Efficacy Variable & Derivation

The primary efficacy endpoint will compare each etrasimod dose (1 and 2 mg) to placebo for:

The proportion of participants achieving clinical remission at Week 12

Clinical remission is defined in Section 16. The SF, RB, and ES subscores will be based on the Mayo Clinic score eCRF, but only if a subscore at baseline in eCRF is missing it will be imputed by corresponding data in Interactive Response Technology (IRT). Participants who achieve clinical remission will be referred to as responders.

Participants who do not achieve clinical remission will be referred to as nonresponders.

# 16.1.2. Missing Data Methods for Primary Efficacy Variable

Participants who:1) discontinue the study for lack of efficacy or adverse event related to UC (data collected for Primary Reason off Study from End of study eCRF and Adverse Events eCRF), 2) initiate a rescue medication for UC, 3) have an increase in dose over Baseline levels in their existing UC medication, or 4) have rescue non-drug treatment (eg, colectomy, ileostomy, or sigmoidectomy) during the study as confirmed after blinded review by clinical and medical team members before study unblinding will be considered to have a known (ie, non-missing) outcome of nonresponse and not as having missing data in the analysis of all efficacy endpoints at any subsequent timepoints, including the primary endpoint. The rescue therapies will be identified by the Arena clinical team during blinded data review. Refer to APPENDIX 5 for the definition of rescue therapies (medication and medical procedures). In scenarios 2 and 3 above, if a subject has an efficacy measurement collected after the initiation or dose increase from Baseline of UC medication, the observed data will be censored at the time of initiation or dose increase and they will be considered as having a nonresponse. Subjects in all 4 scenarios above may still be included in the respective Per Protocol Set, provided they do not violate other criteria for Per Protocol Set. For example, they will be excluded from the Per Protocol Set if they initiate a prohibited medication before the Week 12 efficacy assessment that can affect efficacy of the study treatment and the indication is unrelated to UC.

Document: \\quintiles.net\enterprise\Apps\sasdata\SASb\SAS\Arena\APD334\RZA28116\Biostatistics\Documenta

tion\SAP\503-Final SAP v2.0\APD334-203 SAP Final v2.0-20231120 clean.docx

Author: PPD Version Number: 2.0

Version Date: 20Nov2023

Template No.: CS\_TP\_BS016 Revision 7 Reference: CS\_WI\_BS005

Effective Date: 01Nov2021

Page 35 of 70

Analysis visits will be mapped as per Section 6.4 before any missing data imputation method is applied.

Participants with a missing efficacy outcome will be included in the primary analysis using single imputation as non-responder.

## 16.1.3. Primary Analysis of Primary Efficacy Variable

The primary efficacy analysis will be performed for the FAS with Baseline MMS 5 to 9. Results will be expressed as the number and percentage of participants in clinical remission, difference in clinical remission percentages and 95% CI, odds ratio and associated 95% CI.

## 16.1.4. Supplementary Analysis of Primary Efficacy Variable

The primary analysis as described in Section 16.1.3 using non-responder imputation will be repeated using the mFAS and Per Protocol Set as supplementary analyses in participants with actual Baseline MMS 5 to 9.

The primary analysis as described in Section 16.1.3 will be repeated for the primary endpoint using the FAS with Baseline MMS 4 to 9.

# 16.2. Secondary Efficacy

There is no statistical hypothetical testing of the secondary endpoints.

Secondary efficacy endpoints are defined in Section 16. In general, the primary analysis and supplementary analyses in mFAS planned for the primary endpoints in Sections 16.1.3 and 16.1.4 will be repeated for each secondary efficacy endpoint (Table 3).

Table 3: Planned Analysis by Endpoint

Endpoint	Primary Analysis	Supplementary Analyses in mFAS	Supplementary Analyses in PPS	
Primary endpoints	X	X	X	
Secondary endpoints				
Endoscopic improvement	x	X		
Symptomatic remission	x	x		

Document: \quintiles.net\enterprise\Apps\sasdata\SASb\SAS\Arena\APD334\RZA28116\Biostatistics\Documenta

tion\SAP\503-Final SAP v2.0\APD334-203 SAP Final v2.0-20231120 clean.docx

Author: PPD Version Number: 2.0

Version Date: 20Nov2023

Template No.: CS\_TP\_BS016 Revision 7 Reference: CS\_WI\_BS005

Effective Date: 01Nov2021

Page 36 of 70

Endpoint	Primary Analysis	Supplementary Analyses in mFAS	Supplementary Analyses in PPS
Mucosal healing	X	X	
Clinical response	x	X	
Endoscopic normalization	X	X	

Analyses in the table will be repeated for participants in the FAS with Baseline MMS 4 to 9. mFAS, modified Full Analysis Set.

# 16.2.1. Secondary Efficacy Variables & Derivations

- Endoscopic improvement at Week 12
- Symptomatic remission at Week 12
- Mucosal healing at Week 12
- Clinical response at Week 12
- Endoscopic normalization at Week 12

# 16.2.2. Missing Data Methods for Secondary Efficacy Variables

The same missing data methods used for the primary endpoint described in Section 16.1.1 and Section 16.1.2 will be used for the secondary endpoints.

# 16.2.3. Primary Analysis of Secondary Efficacy Variables

The primary analysis of all the secondary efficacy endpoints will be performed for the FAS with Baseline MMS 5 to 9. For all secondary endpoints, the same analysis that was described in Section 16.1.3 will be performed.

# 16.2.4. Supplementary Analysis of Secondary Efficacy Variables

For all secondary endpoints, the primary analysis as described in Section 16.1.3 using non-responder imputation will be repeated using the mFAS with actual Baseline MMS 5 to 9 as supplementary analyses.

For all the secondary endpoints, primary analyses listed in Table 3 will be repeated in participants using FAS with Baseline MMS 4 to 9.

Document: \quintiles.net\enterprise\Apps\sasdata\SASb\SAS\Arena\APD334\RZA28116\Biostatistics\Documenta

tion\SAP\503-Final SAP v2.0\APD334-203\_SAP\_Final v2.0-20231120\_clean.docx

Author: PPD Version Number: 2.0

Version Date: 20Nov2023

Template No.: CS\_TP\_BS016 Revision 7 Reference: CS\_WI\_BS005

Effective Date: 01Nov2021

PROTOCOL APD334-203

Statistical Analysis Plan

Page 37 of 70

